CBC	Complete blood count
CI	Confidence interval
CL	Clearance
C _{max}	Peak concentration
CNS	Central nervous system
CR	Complete response
CT	Computed tomography
CTLA-4	Cytotoxic T-lymphocyte-associated antigen-4
DLS	Discovery Life Sciences
DLT	Dose-limiting toxicity
DNA	Deoxyribonucleic acid
ECG	Electrocardiogram
ECOG	Eastern Cooperative Oncology Group
EDTA	Disodium edetate dihydrate
EGFR	Epidermal growth factor receptor
Fc	Fragment crystallizable
FDA	Food and Drug Administration
FFPE	Formalin fixed paraffin embedded
FSH	Follicle-stimulating hormone
GCP	Good Clinical Practice
HBV	Hepatitis B virus
HBsAg	Hepatitis B surface antigen
HBsAb, HBcAb	Hepatitis B surface antibody, Hepatitis B core antibody
HCV	Hepatitis C virus
HIV	Human immunodeficiency virus
ICF	Informed consent form
ICH	International Conference on Harmonization
IFN	Interferon
IHC	Immunohistochemistry
IL	Interleukin
IP	Investigational product(s)
irAE	Immune-related adverse event

IRB	Institutional Review Board
IV	Intravenous(ly)
MAb	Monoclonal antibody
MDACC	MD Anderson Cancer Center
MRI	Magnetic resonance imaging
MTD	Maximum tolerated dose
NCI CTCAE	National Cancer Institute Common Terminology Criteria for Adverse Events
NSCLC	Non-small cell lung cancer
OR	Objective response
ORR	Objective response rate
OS	Overall survival
PBMC	Peripheral blood mononuclear cell
PD	Progressive disease
PD-1	Programmed cell death 1
PD-L1	Programmed cell death ligand 1
PD-L2	Programmed cell death ligand 2
PFS	Progression-free survival
PK	Pharmacokinetic(s)
PR	Partial response
Q2W	Every 2 weeks
Q3W	Every 3 weeks
Q4W	Every 4 weeks
Q8W	Every 8 weeks
Q12W	Every 12 weeks
QTc	Time between the start of the Q wave and the end of the T wave corrected for heart rate
QTcF	QT interval on ECG corrected using the Frederica's formula
RCC	Renal cell carcinoma
RD	Repeat dosing
RECIST	Response Evaluation Criteria in Solid Tumors
RNA	Ribonucleic acid
RP2D	Recommended Phase 2 dosing
SAD	Single ascending dose
SAE	Serious adverse event
SD	Stable disease
TEAE	Treatment-emergent adverse event
TIL	Tumor infiltrating lymphocyte
TMG	Toxicity Management Guidelines
TKI	Tyrosine Kinase Inhibitor
T _{max}	Time to peak concentration
TMDD	Target mediated drug disposition
TMG	Toxicity Management Guidelines
TNF- α	Tumor necrosis factor alpha
TSH	Thyroid stimulating hormone
ULN	Upper limit of normal

1. INTRODUCTION

1.1 DISEASE BACKGROUND

1.1.1 EPITHELIAL OVARIAN CANCER

Each year in the United States, over 22,000 women develop ovarian cancer and there are approximately 14,240 attributed deaths annually, making ovarian cancer the deadliest of gynecologic malignancies [1]. Despite high rates of complete response to the combination of tumor reductive surgery and adjuvant platinum-taxane based chemotherapy, the vast majority of patients with stage III/IV EOC recur with a median progression free survival (PFS) of approximately 18 months. In those who recur, despite decades of clinical investigations, most cytotoxic and biological agents result in only modest rates of response and have a typical median PFS of 3 months [2], [3]. Therefore, a crucial unmet need is the development of new strategies that will ultimately improve the overall survival (OS) of patients with EOC.

1.1.2 IMMUNOTHERAPIES

It is increasingly understood that cancers are recognized by the immune system, and, under some circumstances, the immune system may control or even eliminate tumors [4].

PD-L1 is part of a complex system of receptors and ligands that are involved in controlling T-cell activation. The PD-1 receptor (CD279) is expressed on the surface of activated T cells [5]. It has two known ligands: PD-L1 (B7-H1; CD274) and PD-L2 (B7-DC; CD273) [6]. The PD-1 and PD-L1/PD-L2 belong to the family of immune checkpoint proteins that act as co-inhibitory factors, which can halt or limit the development of T cell response. When PD-L1 binds to PD-1, an inhibitory signal is transmitted into the T cell, which reduces cytokine production and suppresses T-cell proliferation. Tumor cells exploit this immune checkpoint pathway as a mechanism to evade detection and inhibit immune response.

PD-L1 is constitutively expressed by B-cells, dendritic cells, and macrophages. Importantly, PD-L1 is commonly over-expressed on tumor cells or on non-transformed cells in the tumor microenvironment[7]. PD-L1 expressed on the tumor cells binds to PD-1 receptors on the activated T-cells leading to the inhibition of cytotoxic T cells. These deactivated T cells remain inhibited in the tumor microenvironment. The PD-1/PD-L1 pathway represents an adaptive immune resistance mechanism that is exerted by tumor cells in response to endogenous anti-tumor activity.

The inhibitory mechanism described above is co-opted by tumors that express PD-L1 as a way of evading immune detection and elimination. The binding of an anti-PD-L1 agent to the PD-L1 receptor inhibits the interaction of PD-L1 with the PD-1 and CD80 receptors expressed on immune cells. This activity overcomes PD-L1-mediated inhibition of antitumor immunity. While functional blockade of PD-L1 results in T-cell reactivation, this mechanism of action is different from direct agonism of a stimulatory receptor such as CD28.

PD-L1 is expressed in a broad range of cancers. Based on these findings, an anti-PD-L1 antibody could be used therapeutically to enhance antitumor immune responses in patients with cancer. Results of non-clinical and clinical studies of monoclonal antibodies (mAbs) targeting the PD-L1/PD-1 pathway have shown evidence of clinical activity and a manageable safety profile, supporting the hypothesis that an anti-PD-L1 antibody could be used to therapeutically enhance antitumor immune response in cancer patients [8]–[11]. Pre-clinical data have now been added to with a wealth of clinical data showing that blockade of negative regulatory signals to T-cells such as cytotoxic T-lymphocyte antigen 4 (CTLA-4) and PD-L1 has promising clinical activity. Ipilimumab was granted United States (US) Food and Drug Administration (FDA) approval for the treatment of metastatic melanoma and is currently under investigation for several other malignancies, whilst nivolumab and pembrolizumab, two anti-PD-1 agents,

and atezolizumab, an anti-PD-L1, agent have been granted approvals by agencies such as the US FDA and the European Medicines Agency approval for the treatment of a number of malignancies including metastatic melanoma, squamous and non-squamous cell non-small-cell lung cancer and urothelial carcinoma. In addition, there are data from agents in the anti-PD-1/PD-L1 class showing clinical activity in a wide range of tumor types.

1.1.3 POTENTIAL UTILITY OF IMMUNE CHECKPOINT INHIBITORS IN OVARIAN CANCER

Immunogenicity of EOC has been well-documented, and there is extensive literature demonstrating the presence of clonally activated CD3+CD8+ TCR $\alpha\beta$ + T-cells in ovarian tumors and their prognostic significance[12]–[18]. Tumor infiltrating lymphocytes (TIL) derived from patients with EOC demonstrate tumor specificity by a) clonal proliferation in response to low concentrations of IL2 in the presence of autologous tumor cells [19] and b) exhibit MHC restricted killing of EOC tumor cell lines as well as cloned autologous tumor cells [18] and c) cytokine production [12], [14], [20]. However, there is also strong evidence that EOC harbors an immune-suppressor environment that includes the presence of regulatory T Cells, CTLA4-positive TILs, monocyte/macrophages, and elevated intratumoral and plasma levels of immunosuppressive cytokines such as IL10, IL6 and TGF β [21]–[26]. Indeed, expression of PDL1 and PDL2 in EOC was shown to correlate with poorer OS[24], and both ascites and peripheral blood derived monocytes from patients with EOC showed upregulated PDL1 expression [26].

1.1.4 POTENTIAL UTILITY OF AXL INHIBITION IN OVARIAN CANCER

As a novel treatment, checkpoint blockade and immune modulation have demonstrated efficacy in heavily pretreated tumors with some durable responses, but only in a small fraction of patients. The emerging data on anti-PD1 / anti-PDL-1 therapies in ovarian cancer demonstrates response rates of 10-15%[8], [27]–[29].

While the mechanism for immune resistance to checkpoint inhibition remains poorly understood, a predictor of response to anti-PD1 therapy is the extent of CD8+ infiltration within the pretreated tumor [30]–[33]. Factors which contribute to T-cell exclusion, and thus resistance, within the tumor microenvironment include immune cell suppression via cytokines, aberrations in antigen presentation, or microenvironmental factors such as hypoxia. The receptor tyrosine kinase AXL has recently been identified as a possible mediator of T-cell exclusion and therapeutic resistance. In multiple tumor types, including uterine serous cancer, head and neck malignancy, and non-small cell lung cancers, AXL expression correlated with poor survival [34]–[37]. In ovarian cancer specifically, a meta-analysis of DNA microarray data and confirmatory cohort demonstrated that AXL ligand GAS6 was highly expressed and correlated to poor survival [38]–[40].

An increasing body of evidence suggests that this survival difference may be due to AXL's suppressive effect on the innate immune response by supporting maturation of natural killer cells and inhibiting macrophage-driven inflammation. AXL has been shown to redirect downstream signaling via STAT1 to result in activation of suppression cytokine signaling proteins [41], and activation of AXL in macrophages leads to a switch from M1 to M2 phenotype resulting in inability to activate CD8 T-cells [42]. Interestingly, AXL has been demonstrated to be induced together with the appearance of drug resistance to both targeted and conventional chemotherapy [34]–[37], [43]–[45]. Therefore, clinical trials utilizing AXL inhibition have been launched for both liquid and solid tumors (NCT02488408, NCT02729298, NCT03454243, NCT02424617).

However, while this signaling axis represents an attractive target for therapeutic intervention, the strong picomolar binding affinity (~14-33 pM) between endogenous GAS6 and AXL and the promiscuity of

small molecule AXL inhibitors has historically presented a barrier to specific and potent inhibition of AXL. AVB-S6-500 is a highly sensitive and specific inhibitor of AXL, with apparent affinity of 93-324 femtomolar to GAS6, which is approximately 200-fold higher affinity than wild-type (WT) AXL. AVB-S6-500 binds GAS6, the sole ligand of AXL, inhibiting its interaction with AXL, thereby dramatically reducing AXL signaled invasion and migration of highly metastatic cells *in vitro* and inhibiting metastatic disease in nonclinical models of aggressive human cancers.

1.1.5 COMBINATION OF IMMUNE CHECKPOINT AND AXL INHIBITION

There is the expectation of synergy between AXL and immune targeting agents[46]. A recent study investigated the genomic profile of anti-PD1 checkpoint-resistant melanoma, and demonstrated that AXL transcript levels were significantly correlated to resistance [47]. Subsequent literature further investigated the role of AXL in checkpoint sensitive and resistant clones and demonstrated that loss of AXL resulted in significantly greater TIL population and subsequent response to radiotherapy and checkpoint immunotherapy[43]. These findings have now been supported with translational mouse models of colon and breast cancer, with markedly decreased tumor growth with dual inhibition of AXL and immune checkpoint inhibition[48]–[50]. Trials utilizing this combination of immune checkpoint inhibition and AXL inhibitor have begun in other solid tumor types, including lung and breast cancer (NCT03184571, NCT03184558).

1.2 DURVALUMAB: NON-CLINICAL AND CLINICAL EXPERIENCE

The non-clinical and clinical experience is fully described in the most current version of the durvalumab Investigator's Brochure.

Durvalumab is a human monoclonal antibody (mAb) of the immunoglobulin G (IgG) 1 kappa subclass that inhibits binding of PD-L1 and is being developed by AstraZeneca/MedImmune for use in the treatment of cancer (MedImmune is a wholly owned subsidiary of AstraZeneca; AstraZeneca/MedImmune will be referred to as AstraZeneca throughout this document). The proposed mechanism of action (MOA) for durvalumab is interference in the interaction of PD-L1 with PD-1 and CD80 (B7.1). Blockade of PD-L1/PD-1 and PD-L1/CD80 interactions releases the inhibition of immune responses, including those that may result in tumor elimination. *In vitro* studies demonstrate that durvalumab antagonizes the inhibitory effect of PD-L1 on primary human T cells resulting in the restored proliferation of IFN- γ [51]. *In vivo* studies have shown that durvalumab inhibits tumor growth in xenograft models via a T-cell-dependent mechanism[51]. Based on these data, durvalumab is expected to stimulate the patient's antitumor immune response by binding to PD-L1 and shifting the balance toward an antitumor response. Durvalumab has been engineered to reduce antibody-dependent cellular cytotoxicity and complement-dependent cytotoxicity.

To date durvalumab has been given to more than 8000 patients as part of ongoing studies either as monotherapy or in combination with other anti-cancer agents. Refer to the current durvalumab Investigator's Brochure for a complete summary of non-clinical and clinical information including safety, efficacy and pharmacokinetics.

1.3 AVB-S6-500: NON-CLINICAL AND CLINICAL EXPERIENCE

AVB-S6-500, a GAS6-AXL pathway inhibitor, is an engineered receptor-Fc fusion protein therapeutic and is being developed by Aravive for use in the treatment of cancer. The proposed MOA for AVB-S6-500 is the high affinity and highly specific binding to GAS6, the sole ligand for AXL, with 200 fold greater affinity compared to native AXL receptor. *In vitro* studies demonstrate that AVB-S6-500 has single agent efficacy in metastatic ovarian cancer models, decreasing both number of metastases and

tumor weight. While the exact mechanism requires further elucidation, prior data suggests that AXL inhibition stimulates a patient's antitumor immune response by decreasing suppressive cytokine signaling and preventing the AXL mediating macrophage switch from the M1 to the M2 phenotype. Additionally, AVB-S6-500 proposed anti-fibrotic effects may benefit desmoplasia and drug penetrance.

When directly compared in nonclinical models with the most advanced selective anti-AXL small molecules currently in clinical development, AVB-S6-500 achieved superior antitumor efficacy while displaying no toxicity in pharmacology studies [52]. AVB-S6-500 causes regression of tumor cells in vivo when dosing in these models commenced 4-7 days after tumor inoculation and establishment of small tumors in the mouse. However, AVB-S6-500 is not directly cytotoxic in vitro and under normal physiological (nonstressed) conditions, as the in vitro IC50 in cancer cells (with high levels of AXL on the cell surface) is $> 100 \mu\text{M}$. Modulation of AXL signaling by a predecessor AXL decoy receptor protein, MYD1 Fc (AXL-S6-1 hIgG), increased expression of the epithelial marker E-cadherin, consistent with the AXL decoy protein causing a mesenchymal to epithelial phenotype transition in vivo [52]. Reversal of the mesenchymal phenotype has been reported to cause growth inhibition, suppression of spheroid forming capacity and induction of apoptosis[53], [54]. This is consistent with the combination treatment studies conducted with predecessor proteins, which demonstrated a relationship between AXL signaling and the cellular response to DNA damage in breast, pancreatic and ovarian cancer models. The damage was observed more so in combination with cytotoxic chemotherapies such as doxorubicin and gemcitabine[52]. Thus, inhibiting the AXL/GAS6 pathway in stressed cells (due to transition from mesenchymal to epithelial phenotype and/or in combination with cytotoxic agents) appears to lead to cell death in vivo.

Safety data from the Phase 1 first-in-human study in healthy volunteers indicate that AVB-S6-500 was very well tolerated across all administered doses and a MTD was not reached. In addition to safety and tolerability, serum levels of AVB-S6-500 (pharmacokinetic [PK] data) and serum GAS6 levels (pharmacodynamics data) were used to identify the active doses of AVB-S6-500 that fully suppress serum GAS6 and guided selection of doses to be tested in combination with the standard-of-care (SOC) therapies in Phase 1b/2 studies in cancer patients. Refer to Investigational Brochure for complete details.

1.4 RESEARCH HYPOTHESIS

Our overarching hypothesis is that the addition of AXL inhibition via the novel agent AVB-S6-500 to durvalumab (MEDI4736) therapy will produce clinically significant improvement in response rate compared to the currently achievable response rate with programmed cell death protein 1 (PD1) immune inhibition alone in patients with platinum resistant epithelial ovarian, fallopian tube and primary peritoneal cancers (that will be collectively referred to as EOC). We hypothesize that this combination will be associated with an acceptable toxicity profile. Additionally, dual targeting of programmed cell death protein ligand 1 (PDL1) and AXL in combination may synergistically prolong time to progression. In an exploratory analysis we will also compare translational objectives, to investigate molecular and immunologic changes associated with the combination of AVB-S6-500 and durvalumab.

1.5 RATIONALE FOR CONDUCTING THIS STUDY

1.5.1 AVB-S6-500 DOSE

Based on available data from a recently completed First-in-Human, Phase 1 study in healthy volunteers (AVB500-HV-001), PK and pharmacodynamics data for AVB-S6-500 were evaluated in real time using validated enzyme linked immunosorbent assays (ELISA) in each cohort. As expected with an IV administered drug, Cmax increased proportionally to dose and Tmax was 1 h (the earliest time point

collected) for all doses. Consistent with target mediated drug disposition (TMDD), the area under the curve (AUC) increased more than proportionally across doses and the half-life increased across doses. At the lowest dose tested, 1 mg/kg, serum GAS6 levels were suppressed (below level of quantitation [BLQ] of 2 ng/mL) for one-week post-dose in 4 out of 6 subjects. All 6 subjects in the 2.5 and 5 mg/kg groups had serum GAS6 levels BLQ 1-week post dose. All 6 subjects in the 5 mg/kg had serum GAS6 levels BLQ 2 weeks post dose. A single 10 mg/kg dose suppressed serum GAS6 for at least 3 weeks. Thus, all single doses tested had the desired pharmacological activity. In addition, GAS6 levels were suppressed for 3 weeks after the 4th dose of 5 mg/kg in the RD portion of the study.

The dosing regimen that will be tested in the current trial is therefore 10 mg/kg every other week. The AVB-S6-500 concentrations vs the serum GAS6 levels are shown in the **Figure 1** for this recommended dosing. This dose is anticipated to provide abrogation of serum GAS6 for at least 14 days and maintain the AVB-S6-500 levels in blood above those needed for 90% saturation of GAS6. Additionally, as above, subjects in the 5 mg/kg dosing also had serum GAS6 levels BLQ at 2 weeks post-dose. Thus, all doses intended during the current study, including dose de-escalation, had the desired pharmacological activity.

In terms of safety, review of safety data from first-in-human study suggests that IV doses of up to 10 mg/kg of AVB-S6-500 have been well tolerated. No serious adverse events (SAEs), deaths or withdrawals from study due to AEs have been reported. The incidence of treatment-emergent AEs (TEAE) does not appear to increase with dose.

However, if tolerability issues unexpectedly arise for the AVB-S6-500 combination with Durvalumab, there is opportunity to adjust the AVB-S6-500 dose prior to enrolling the combination cohort. If, after review of the first cycle safety data from 3 subjects, the regimen of 10 mg/kg AVB-S6-500 every 2 weeks (Q2W) is deemed not well-tolerated in combination with Durvalumab, 3 new subjects will be enrolled into a cohort with a lower AVB-S6-500 dose of 5 mg/kg with weekly dosing (the durvalumab dose would remain unchanged).

[figure not shown]

Figure 1. PK/PD for the 10 mg/kg Cohort

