3.1 END OF STUDY ENROLLMENT

In the first quarter of 2021, study supporters Aravive and AstraZeneca made the decision to end enrollment based on available data after the 5th evaluable subject completed treatment on the safety lead-in.

[figure not shown]

Figure 2. Study Schema

Dosing schedule as above demonstrates investigational product at week of administration, where A = AVB-S6-500 monotherapy, D= durvalumab monotherapy, and A+D = AVB-S6-500 + durvalumab combination therapy

* Patients receiving the recommended Phase 2 dose (RP2D) will then be included in the primary analysis of the combination therapy. However, these patients will continue on the Safety Lead-in dosing schedule and will not participate in the Phase 2 monotherapy. See de-escalation dosing regimens below.

† Sample size calculations account for predicted 8% dropout rate due to toxicity.

‡ Dosing schedule shown reflects the starting dose for the dose escalation. This may be adjusted for the de-escalation schedule below and determination of the RP2D.

Table 1. Dosing for Dose Escalation

Dose Level	Durvalumab + AVB-S6-500
Dose Level 0 (Initial dose)	durvalumab (1500mg Q4W), AVB-S6-500 (10mg/kg Q2W)
Dose level 1	durvalumab (1500mg Q4W), AVB-S6-500 (15mg/kg Q2W)
Dose level 2	durvalumab (1500mg Q4W), AVB-S6-500 (20mg/kg Q2W)

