6.2 DEFINITION OF DOSE-LIMITING TOXICITIES

DLTs will be evaluated during the safety lead-in (dose de-escalation phase) of the trial. The period for evaluating DLTs will be from the time of first administration of study drug until 6 weeks (1.5 cycles). Any treatment-related toxicities that first occurred during the DLT period must be followed for resolution to determine if the event qualifies as a DLT as specified in the DLT criteria below. Patients who do not remain on the study up to this time for reasons other than DLT will be replaced with another patient at the same dose level. Grading of DLTs will follow the guidelines provided in the Common Terminology Criteria for Adverse Events (CTCAE) version 5.0.

To be considered a DLT, an AE must be at least possibly related to the investigational product or regimen and meet the criteria listed below. Toxicity that is clearly and directly related to the primary disease or to another etiology is excluded from this definition. The DLT criteria are specified in the following lists.

Hematologic toxicity:

- Grade ≥ 3 neutropenia complicated by fever $>38.3^{\circ}\text{C}$
- Grade ≥ 3 neutropenia that does not improve \leq Grade 1 within 7 days
- Grade 4 neutropenia (lasting more than 7 days)
- Grade ≥ 3 thrombocytopenia with significant bleeding
- Grade 3 thrombocytopenia that is not associated with clinically significant bleeding and does not improve by at least 1 grade within 7 days
- Grade 4 thrombocytopenia (regardless of duration)
- Grade 4 anemia (regardless of duration)

Non-hematologic toxicity:

- Any Grade 4 non-immune-mediated AE
- Any Grade 4 immune-mediated AE, excluding endocrinopathies
- Any Grade 3 non-immune mediated AE, including fatigue, that does not resolve to \leq Grade 1 or baseline within 30 days with optimal medical management
- Any Grade 3 immune-mediated AE – excluding diarrhea/colitis, pneumonitis, hepatitis, rash, neurotoxicity, myocarditis, myositis/polymyositis, endocrinopathies and nephritis – that does not resolve to \leq Grade 2 or baseline within 15 days and to \leq Grade 1 within 30 days after onset of the event, despite optimal medical management including systemic corticosteroids

- Grade 3 diarrhea or colitis
- Grade 3 noninfectious pneumonitis
- Grade 2 noninfectious pneumonitis that does not resolve to \leq Grade 1 within 3 days of the initiation of maximal supportive care

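### Sections 1.5.1, 6.1 and 6.2 describe one 10 mg/kg Q2W regimen that can only be lowered, while Table 1, Section 3.2 and Section 9 escalate to 15 and 20 mg/kg, above the human doses this document reports

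*Combined protocol and SAP*

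**What the plan says.** Section 1.5.1 settles on one regimen: "The dosing regimen that will be tested in the current trial is therefore 10 mg/kg every other week". Its only alternative, if that regimen is not well tolerated after the first cycle in 3 subjects, is a lower dose of 5 mg/kg given weekly to 3 new subjects. It concludes: "Thus, all doses intended during the current study, including dose de-escalation, had the desired pharmacological activity".

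Section 6.2 labels the lead-in accordingly: "DLTs will be evaluated during the safety lead-in (dose de-escalation phase) of the trial". Section 6.1 uses the same label.

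Table 1, whose title refers to dose escalation, starts at Dose Level 0 (10 mg/kg Q2W), goes to level 1 (15 mg/kg Q2W), and ends at level 2: "durvalumab (1500mg Q4W), AVB-S6-500 (20mg/kg Q2W". It has no 5 mg/kg level. Section 3.2 says the trial opens with dose escalation. Section 9 gives BOIN rules for moving up or down among levels numbered 1 to 3, with the first cohort at level 1. It names no mg/kg values.

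The human data in Section 1.5.1 come from the healthy-volunteer study. Safety is summarised as: "IV doses of up to 10 mg/kg of AVB-S6-500 have been well tolerated".

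**The concern.** Two dosing plans stand side by side in current text. In one, 10 mg/kg Q2W is the highest dose and the only move is downward. In the other it is the lowest dose and the moves are upward. This is more than a labelling slip, because the two plans call for different actions once the first cohort is read out.

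The dose rationale was also written for the first plan. Its statements on activity and tolerability are the ones against which the lead-in safety results will be read, and they do not reach two of the three levels that Table 1 allows.

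**Working it through.** **1. The two plans compared**

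| Item | Sections 1.5.1, 6.1, 6.2 | Table 1, Sections 3.2 and 9 |
|---|---|---|
| Doses of AVB-S6-500 | 10 mg/kg Q2W; 5 mg/kg weekly as fallback (1.5.1) | 10, 15, 20 mg/kg Q2W (Table 1) |
| Direction | De-escalation | Escalation from the lowest level |
| Starting dose not tolerated | New cohort at the lower dose (1.5.1) | Stay at the lowest level, or stop (Section 9) |
| Level numbers | None | 0 to 2 in Table 1; 1 to 3 in Section 9 |

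The footnotes to Figure 2 refer to both an escalation and a de-escalation schedule below, but the table that follows contains no lower dose.

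**2. Is Section 9 really an upward design?** The BOIN boundaries were recomputed at the stated target φ = 0.25 with φ1 = 0.6φ = 0.15 and φ2 = 1.4φ = 0.35:

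- Escalation: ln(0.85/0.75) / ln[(0.25 × 0.85)/(0.15 × 0.75)] = 0.197
- De-escalation: ln(0.75/0.65) / ln[(0.35 × 0.75)/(0.25 × 0.65)] = 0.298

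With elimination when Pr(p > 0.25 | data) > 0.95 under a Beta(1,1) prior, all 36 cells of Table 12 are reproduced. A 10,000-trial simulation (three levels, start at the lowest, cohorts of 3, maximum 15) gives mean sample sizes of 11.91, 14.26 and 14.82, against 11.75, 14.08 and 14.75 in Table 13. Section 9 is therefore a three-level escalation from its lowest dose. (The cut-offs printed in the Section 9 text differ from those behind Table 12. That is a separate matter.)

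**3. Where the rules diverge in practice.** For 3 patients, Table 12 de-escalates at 1 or more DLTs and eliminates at 3. At the lowest level:

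- With 1 or 2 DLTs in 3, Section 9 keeps treating at that level.
- With 3 DLTs in 3, Section 9 stops the trial.

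In either case Section 1.5.1 would open the 5 mg/kg weekly cohort if the regimen is judged not well tolerated. Section 9 cannot reach that cohort.

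**4. Level numbering.** Section 9 puts the first cohort at level 1. Table 1 calls 10 mg/kg Dose Level 0 and gives the number 1 to 15 mg/kg.

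**5. Which levels do the reported human data cover?** Section 1.5.1 reports these doses:

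- 1 mg/kg: "At the lowest dose tested, 1 mg/kg, serum GAS6 levels were suppressed" for one week in 4 of 6 subjects.
- 2.5 and 5 mg/kg: "All 6 subjects in the 2.5 and 5 mg/kg groups had serum GAS6 levels BLQ 1-week post dose".
- 10 mg/kg: "A single 10 mg/kg dose suppressed serum GAS6 for at least 3 weeks".
- Repeat dosing: 5 mg/kg only, with no interval stated.

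Ratios to the highest reported human dose are 15/10 = 1.5 and 20/10 = 2.0. Against the repeat dose, 20/5 = 4.0 dose for dose. Per unit of time the ratio depends on the unstated interval. If the repeat doses were Q2W it is 4.0; if weekly, it is (20/2)/5 = 2.0. Both intervals are assumptions.

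**6. Share treated above the lowest level (Table 13)**

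- Scenario 1: (3.0 + 0.6)/11.75 = 31%
- Scenario 2: (5.0 + 2.4)/14.08 = 53%
- Scenario 3: (5.1 + 4.9)/14.75 = 68%

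These patients would be at 15 or 20 mg/kg if Table 13's level 1 is Table 1's 10 mg/kg level.

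**The case against.** The best defence has four parts.

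**The text is historical.** Section 3 is headed as the original design, and Section 9 says that part of the text no longer applies. However, that statement refers to the text below it, on randomization and Phase II. It does not retire Table 1 or the dose-finding rules.

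**Accrual is over.** Section 3.1 says enrollment ended after the fifth evaluable lead-in subject. This stands, and it lowers the urgency: what remains is mainly the accuracy of the record.

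**Nobody would be misled.** The escalation text is explicit, Sections 6.1 and 6.2 give no mg/kg value for AVB-S6-500, one recruiting institution is named, and Section 9.2.3 requires IND Office approval before a dose level changes. This also stands in part. It would go too far to say that sites would expect no exposure above 10 mg/kg. But an approval step does not say which of two conflicting rules is to be approved.

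**The safety data are favourable.** No MTD was reached in healthy volunteers (Section 1.3). In Section 1.5.1, Cmax rose in proportion to dose and adverse event incidence did not appear to rise with dose, although AUC rose more than proportionally. These findings are relevant to the rationale, but they describe the doses given, and the doses reported stop at 10 mg/kg.

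A reader might infer that 15 and 20 mg/kg exceed every dose ever tested in humans. The documents do not establish this. They refer to the Investigator's Brochure for full data, and it is not available here. A reader might also cite Appendix C as calling the lead-in a de-escalation. It says only that durvalumab is not modified in dose de-escalation, a step that Section 9 also contains.

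**Conclusion.** The contradiction is real and sits in current text. The plan disagrees with itself on the dose set, the direction of the lead-in, the level numbers, and the response if the starting dose is poorly tolerated. The statement that all intended doses were active has no support in this document for two of the three Table 1 levels, and the tolerability statement does not reach them. The top level is 2.0 times the highest human dose reported here. The multiple of the repeat dose cannot be fixed without its interval.

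The 31% to 68% range is a set of simulated averages under Table 13's assumed DLT rates. It should not be read as expected enrollment or as a count of patients who received 15 or 20 mg/kg, because Section 3.1 does not say which level the five evaluable subjects received. Nor does the numbering conflict show that dosing began at 15 mg/kg: Table 1 marks 10 mg/kg as the initial dose and Section 9 starts at its lowest level. The labels still conflict if read literally.

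This should be corrected, mainly so that the dose rules and their rationale are on record correctly. No view is taken on which dose or rule is right.

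**What to change.** - Reconcile Section 1.5.1, Section 3 (Table 1, the Figure 2 footnotes and 3.2), Sections 6.1 and 6.2, and Section 9. All should state the same dose set, level numbering, direction, and response to poor tolerability at the starting dose.
- Limit the sentence on the activity of all intended doses to those with data.
- If levels above 10 mg/kg stay, give the human data or other basis for them in Sections 1.5.1 and 1.6.2.1, or state that there is none. Do not write that they exceed all doses tested in humans unless the Investigator's Brochure bears that out.

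The cost is a text amendment with the approvals that Section 10.4 requires. It needs no new patients or procedures.
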